6.5.8 Deviations in Analyses from Study Protocol	

List of Abbreviations

AE adverse event

ALT (SGPT) alanine transaminase (serum glutamate pyruvate

transaminase)

AST (SGOT) aspartate transaminase (serum glutamic oxaloacetic

transaminase)

ARR annualized relapse rate

BUN blood urea nitrogen

CRF case report form

Gd gadolinium

GGT gamma-glutamyl-transferase

EDSS Expanded Disability Status Scale

EQ-5D EQ-5D Health Survey

GA glatiramer acetate

HDL high-density lipoprotein

HLGT high-level group term

HLT high-level term

IXRS Interactive Voice and Web Response System

INEC Independent Neurology Evaluation Committee

LDL low-density lipoprotein

MedDRA Medical Dictionary for Regulatory Activities

MRI magnetic resonance imaging

MS multiple sclerosis

MTR Magnetization Transfer Ratio
PBVC Percent Brain Volume Change

PT preferred term

SAE serious adverse event

SAP Statistical Analysis Plan

SOC system organ class

SF-36[®] Health Survey

ULN upper limit of normal

VAS Visual Analogue Scale

VFT Visual Function Test

WBC white blood cell

WHO World Health Organization

1 STUDY OBJECTIVES AND ENDPOINTS

1.1 Primary Objective and Endpoint

The primary objective of the study is to evaluate the long-term safety profile of BG00012.

1.2 Secondary Objectives and Endpoints

The secondary objectives of this study are as follows:

- To evaluate the long-term efficacy of BG00012 using clinical endpoints (including relapse and ARR) and disability progression (Expanded Disability Status Scale [EDSS]).
- To evaluate further the long-term effects of BG00012 on MS brain lesions on MRI scans in subjects who had MRI scans as part of Studies 109MS301 and 109MS302.
- To evaluate the long-term effects of BG00012 on health economics assessments and the visual function test (VFT). The endpoints are the Short-form 36 Health Survey (SF-36) and EuroQol EQ-5D Health Survey (EQ-5D) quality of life questionnaires, and the visual function test scores.

1.3 Exploratory Objectives and Endpoints

The exploratory objectives of this study are as follows:

2 STUDY DESIGN

2.1 Study Overview

The first phase of this extension study is a multicenter, parallel-group, randomized, dose-blind, dose-comparison study. The second phase of the study is an open-label phase during which all subjects receive BG00012 at a dose of 240mg BID. A total of 1738 subjects with relapsing-remitting multiple sclerosis have been randomized at approximately 375 sites in North America, Europe, and the rest of the world.

Eligible subjects from Studies 109MS301 and 109MS302 were enrolled in this extension study and were followed for up to 8 years, assuming BG00012 continues to have a positive benefit/risk ratio.

All subjects received either:

- BG00012 240 mg BID (2 capsules [120 mg each] twice a day and 2 placebo capsules once a day); or
- BG00012 240 mg TID (2 capsules [120 mg each] 3 times a day).

Subjects randomized to BG00012 in Study 109MS301 or 109MS302 continued on the same BG000012 dose in this extension study.

Subjects randomized to placebo in Study 109MS301 or 109MS302 or glatiramer acetate (GA) in Study 109MS302 were randomized to BG00012 in a 1:1 ratio to 240 mg BID or 240 mg TID in this extension study.

With regulatory approval (effective March 2013), all patients receiving BG00012 240 mg TID switched to BID (approved dosage) at their next study visit. This study became an open label extension study with the approved dosage BG00012 240 mg BID.

Subjects who switched to an alternate approved MS therapy in Study 109MS301 or 109MS302 were randomized/enrolled in this extension study as outlined above according to their original treatment group in 109MS301 or 109MS302.

2.2 Overall Study Duration and Follow-Up

Eligible subjects were enrolled at Week 96 (Visit 24) of their previous BG00012 study (109MS301 or 109MS302), which would serve as the Baseline Visit for this extension study. If the Baseline Visit could not be combined with Visit 24 of their previous BG00012 study, the subjects may have been randomized within 6 months of Visit 24, provided that they still were eligible for enrollment. The Baseline visit assessments may have been repeated if there was a gap in study treatment.

Subjects reported to the study site every 4 weeks for the first 24 weeks (Visit 1 through Visit 6) and every 12 weeks thereafter for up to 8 years.

Subjects who completed the Week 384 visit (Visit 36), regardless of further need to monitor lymphocytes on study, completed an End of Study Visit at Week 388 ± 7 days. For subjects who have completed Visit 36, an End of Study Visit was completed 4 weeks after their next visit (scheduled or unscheduled), regardless of further need to monitor lymphocytes on study. Subjects who permanently discontinued BG00012 prior to Week 384, regardless of further need to monitor lymphocytes on study, completed a Premature Study Treatment Withdrawal Visit within 4 weeks after their last dose of BG00012. Subjects who completed BG00012 treatment or permanently discontinued BG00012 for any reason and who had a lymphocyte count <LLN were not withdrawn from the study. These subjects were followed according to Protocol Section 11.3.

For subjects who have already completed Visit 36 (or beyond) prior to the Protocol Version 8, an End of Study Visit was completed 4 weeks after their next visit (scheduled or unscheduled), regardless of further need to monitor lymphocytes on study. For subjects who have not completed Visit 36 prior to Protocol Version 8, Visit 36 served as the last scheduled Visit and an End of Study Visit was completed 4 weeks after their next visit (scheduled or unscheduled), regardless of further need to monitor lymphocytes on study.

Premature Study Withdrawal Visits and Unscheduled Relapse Assessment Visits were performed as necessary. All efforts were made to keep the subjects' visit schedule relative to their Baseline Visit (Day 1). All subjects who discontinued the study treatment were considered to be prematurely withdrawn from the study.

The end of study is defined as the Last Patient, Last Visit for final collection of data for the primary outcome

2.3 **MRI**

MRI was performed in the same subset of sites/countries as in Studies 109MS301 and 109MS302, which was based on the availability of MRI equipment at the sites to perform the assessments required for the study (e.g., MTR). All subjects at the MRI sites were offered the option to participate in Studies 109MS301 and 109MS302, and those subjects continuing into Study 109MS303 continued their participation in the MRI cohort. MRI scans were performed on a yearly basis in Study 109MS303, as well as at the time of premature withdrawal up through and including Amendment 6.

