## **7. STUDY DESIGN**

### **7.1. Study Overview**

This first phase of this extension study is a multicenter, parallel-group, randomized, dose-blind, dose-comparison. The second phase of the study is an open-label phase during which all subjects receive BG00012 at a dose of 240 mg BID. Approximately 1700 subjects have been enrolled at approximately 375 sites in North America, Europe, and the rest of the world.

It is intended that eligible subjects from Studies 109MS301 and 109MS302 will be followed for at least 8 years in this extension study, assuming BG00012 continues to have a positive benefit-risk ratio. At enrollment into the study, all subjects received either:

- BG00012 240 mg BID (2 capsules [120 mg each] twice a day and 2 placebo capsules once a day).

OR

- BG00012 240 mg TID (2 capsules [120 mg each] 3 times a day).

Subjects randomized to BG00012 in Study 109MS301 or 109MS302 continued on the same BG00012 dose in this extension study.

Subjects randomized to placebo in Study 109MS301 or 109MS302 or to GA in Study 109MS302 were randomized to BG00012 240 mg BID or 240 mg TID at a 1:1 ratio in this extension study.

Subjects who switched to an alternate approved MS therapy in Study 109MS301 or 109MS302 were randomized in this extension study as outlined above according to their original treatment group in Study 109MS301 or 109MS302.

All subjects continuing in this extension study are currently receiving the currently marketed dose of BG00012 240 mg BID (2 capsules [120 mg each] BID). Subjects randomized to BG00012 240 mg TID were switched to BID dosing (2 capsules [120 mg each] BID) following BG00012 approval.

Subjects who complete BG00012 treatment or permanently discontinue BG00012 for any reason and who have a lymphocyte count less than the lower limit of normal (<LLN) should not be withdrawn from the study. These subjects will be followed according to Section 11.3.

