## **PRIMARY REASON(S) FOR AMENDMENT**

The primary reason for this amendment to Protocol 109MS303 is extension of the duration of the study from 2 years to 5 years or marketing authorization (if approved), whichever occurs first.

New text is shown in **bold** type; deleted text is shown with a ~~striketrough~~.

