6.3.2 Accounting of Subjects

The following categories of accounting will be summarized for Study 109MS303 using numbers and percentages:

- Subjects who entered the study;
- Subjects who were dosed;
- Subjects who discontinued treatment (and therefore withdrew from study), along with reasons for discontinuing treatment; and
- Subjects who have lymphocyte follow up.

Listings of subjects who discontinued treatment and withdrew from the study and the reasons for discontinuation/withdrawal will be presented.

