6.3.6 Study Drug Compliance and Time on Study

Study drug compliance in Study 109MS303 will be summarized. The number of capsules not taken since the previous visit (out of those capsules the subject was expected to take) is collected on the study drug accountability CRF page. Using this information, percentage compliance will also be calculated as follows:

Total number of capsules not taken is calculated as the sum of all individual values of the number of capsules not taken since the previous visit for a subject, as defined above.

Total number of capsules assigned is calculated based on the number of days on study medication for a subject. The calculation of number of days on study medication is detailed below.

Percentage compliance is then calculated as: [(Total number of capsules assigned) – (Total number of capsules not taken)] / (Total number of capsules assigned) * 100.

Percentage compliance will be calculated up to the date of last dose in Study 109MS303.

In addition, the total time on study medication will be summarized as a continuous variable and categorized into intervals. Days on study medication is calculated as the number of days from date of first dose to date of last dose. Additionally, the total number of subject-years of exposure to study medication will be presented. Time on study medication will be summarized for Study 109MS303 only and for Combined Data, utilizing the Study 109MS303 ITT and Safety populations.

Time on study parameters, including overall time on study and time on study prior to first use of alternative MS medication, will be summarized as a continuous variable and categorized into intervals. Total number of subject-years for time on study, both overall and prior to first use of alternative MS medication, will also be presented with respect to the dataset analyzed. The last known date on study will be taken as the last visit/evaluation date from relevant data for a subject. Summaries will be performed for Study 109MS303 only and for Combined Data, utilizing the Study 109MS303 ITT population. Additionally, overall time on study in Study 109MS303 will be summarized utilizing the Study 109MS303 Safety population.

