6.5.3 Analysis of Adverse Events

All summary analyses of AEs will be based on the principle of treatment emergence. In a given dataset, an event is considered to be treatment emergent if it has an onset date on or after the date of first study treatment or if it was present prior to start of study treatment and subsequently worsened. Henceforth, whenever an analysis or summary of AEs is mentioned, it is intended that this is in reference to the treatment emergent adverse event experience, even if not explicitly mentioned.

In general, analyses of AEs will include all events through the end of a subject's follow-up in a given dataset.

In general, AEs will be analyzed based on *incidence*, defined as the proportion of subjects who had at least one occurrence of an event out of the number of subjects in the relevant safety analysis population.

The Medical Dictionary for Regulatory Activities (MedDRA) version 13.1 will be utilized to code and group AEs by System Organ Class (SOC) and Preferred Term (PT). References to summaries of AEs using System Organ Class are intended to refer to the primary SOC. In addition to summaries of incidence by both SOC and PT, incidence of adverse events may also be summarized and presented by SOC only or by PT only, as appropriate, depending on the nature of the analysis performed. Adverse event summaries may also be provided by

High-Level Group Term (HLGT) or High-Level Term (HLT), if considered appropriate for signal detection, in instances where the SOC level of summary is too broad but the PT level of summary is too granular.

A summary analysis of adverse events will be provided including the following numbers and incidences/percentages of subjects: in the safety analysis population; with an adverse event; with a moderate or severe AE; with a severe AE; with a related AE; with a serious adverse event (SAE); with an AE leading to discontinuation of study treatment; and with an AE leading to withdrawal from study.

Summaries of the most frequently reported AEs by PT will also be presented, defined as those AEs with an incidence of AEs of at least 5% (at SOC or PT level) in any treatment group. Other cutoff values may be explored, as appropriate.

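### SAP 2.2 and 6.3.2 count every treatment discontinuer as withdrawn from the study, contradicting SAP 2.2 itself and the protocol for subjects who stop with lymphocytes below LLN

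*SAP*

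**What the plan says.** SAP 2.2 gives two rules. The first covers subjects who completed treatment or stopped it permanently: those who "permanently discontinued BG00012 for any reason and who had a lymphocyte count <LLN were not withdrawn from the study", and who were then followed under Protocol 11.3. The second comes two paragraphs later and has no exception: "All subjects who discontinued the study treatment were considered to be prematurely withdrawn from the study".

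The protocol supports the first rule. Section 7.1 says that a subject who completes or permanently stops BG00012 with "a lymphocyte count less than the lower limit of normal (<LLN) should not be withdrawn from the study". Sections 7.2.3 and 11.1 repeat this. Section 11.4 lists the reasons for stopping treatment and leaving the study, then exempts subjects below LLN in a note. It also requires the dates and reasons for both events in the CRF.

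SAP 6.3.2 follows the second rule. One accounting category is "Subjects who discontinued treatment (and therefore withdrew from study), along with reasons for discontinuing treatment". The same section has a separate category for subjects with lymphocyte follow-up, and plans listings of the reasons for discontinuation or withdrawal.

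SAP 6.5.3 treats the two events as different outcomes. Its AE overview counts subjects "with an AE leading to discontinuation of study treatment; and with an AE leading to withdrawal from study", and tables by SOC and PT follow for each. It does not say how the withdrawal outcome is derived.

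**The concern.** Stopping treatment and leaving the study are different events in this trial. A subject who stops below LLN can remain in follow-up for up to 48 weeks after the last dose, or up to 96 weeks in some cases under Protocol Table 3. A plan that merges the two events for all subjects, while also keeping them apart for this group, leaves study withdrawal without a unique definition.

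The outputs at stake are disposition and AE-related withdrawal, both of which serve the primary objective of long-term safety. The affected group is defined by low lymphocytes, and lymphopenia is among the AE categories of special interest in SAP 6.5.3.

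**Working it through.** The documents state no withdrawal count or incidence, so there is no figure to reproduce. The check sets the texts side by side.

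| Place | Is a subject who stops BG00012 below LLN withdrawn? |
|---|---|
| Protocol 7.1, 7.2.3, 11.1, 11.4 (note) | No; followed under 11.3 |
| SAP 2.2, earlier paragraph | No; followed under Protocol 11.3 |
| SAP 6.5.6 | Visits, assessments and lymphocyte follow-up continue |
| SAP 2.2, later paragraph | Yes; no exception |
| SAP 6.3.2 | Yes; discontinuation is equated with withdrawal |

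The two SAP 2.2 statements cannot both hold for a subject below LLN. For discontinuers at or above LLN they agree, because Protocol 11.4 has those subjects withdrawn. The conflict is therefore confined to stops below LLN.

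Consequences, output by output:

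1. **Treatment discontinuations (6.3.2).** The row counts subjects who stopped treatment. That number is the same under either rule. Only the attached statement that they also left the study is wrong for subjects below LLN.
2. **Study withdrawal (6.3.2).** Under the rule without an exception, a subject below LLN is reported as withdrawn at the treatment stop while still being followed. Reasons are tabulated only for stopping treatment; reasons for leaving the study appear in a listing.
3. **AE outputs (6.5.3).** If every discontinuer is withdrawn, every AE leading to discontinuation also leads to withdrawal. Leaving the study also ends study treatment, so the reverse holds too. The two overview rows and the two SOC/PT tables then contain the same subjects. Under the protocol's rule they can differ.
4. **Time on study (6.3.6).** This does not use a withdrawal flag: "The last known date on study will be taken as the last visit/evaluation date from relevant data for a subject". It is unaffected.
5. **AE incidence (6.5.3).** Events count through the end of each subject's follow-up. It is unaffected.

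The number of subjects classified differently would be N × (share who discontinue) × (share of those below LLN). N = 1738 (SAP 2.1). The documents give neither share. Purely as assumptions, 30% and 10% give 1738 × 0.30 × 0.10 ≈ 52, and 60% and 40% give 1738 × 0.60 × 0.40 ≈ 417. An eightfold spread from assumed inputs is not an estimate, so no count is claimed.

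**The case against.** The best defence is that this is a wording slip with little reach. The discontinuation count is right under either rule. SAP 6.3.2 already has a lymphocyte follow-up row and a listing of withdrawal reasons, so the affected subjects are partly visible. Nothing in 6.5.3 ties the AE-withdrawal flag to the SAP 2.2 sentence, and a programmer who uses the CRF reason can classify these subjects correctly. The protocol also blurs the boundary: Sections 4.6 and 14.3.5 make the Premature Study Treatment Withdrawal Visit serve as the End of Study Visit, so the SAP sentence could be an accounting convention.

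Most of this stands, and it limits the point. It does not remove it. A convention that contradicts both the same SAP section and the note in Protocol 11.4 would have to be declared as one, and 6.3.2 carries it into a reported table.

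A reader might infer more than the documents support:

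- *That the AE-withdrawal tables are wrong.* This is not shown, because the SAP does not name the source of the flag.
- *That stops required by Table 3 count entirely as lymphopenia-related study withdrawal under one rule and not at all under the other.* Status at the treatment stop does differ. But these subjects leave the study later, and no text prevents lymphopenia from being recorded as the reason then.
- *That subjects who reached the planned end of an early protocol version are forced into the discontinued row.* This rests on amendment text that has been superseded, and nothing shows that any subject ended that way.

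**Conclusion.** The point holds as an error of wording that reaches an analysis section. SAP 2.2 contradicts itself and the protocol on whether subjects who stop below LLN are withdrawn, and SAP 6.3.2 uses the version that the protocol does not support. If the plan is applied as written, study withdrawal is misreported for these subjects and the two AE outputs in 6.5.3 become redundant.

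The impact is small. It is limited to stops below LLN and to the study-withdrawal label, its reasons and the AE-withdrawal outputs. The number of subjects cannot be derived from the documents. The conclusion assumes only that programming follows the SAP text; if the CRF withdrawal reason is used instead, the AE tables can be correct, but the SAP would still need to say so.

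**What to change.** - In SAP 2.2, add the below-LLN exception to the later sentence, or delete that sentence.
- In SAP 6.3.2, remove the parenthesis that equates stopping treatment with leaving the study. Tabulate end of treatment and end of study separately, each with its own reasons, and keep the lymphocyte follow-up row.
- In SAP 6.5.3, state that AEs leading to study withdrawal are taken from the study-withdrawal reason in the CRF.
- Reconcile these changes with Protocol 4.6 and 14.3.5, where the Premature Study Treatment Withdrawal Visit serves as the End of Study Visit, so that the end-of-study date is unambiguous for subjects still in lymphocyte follow-up.

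The cost is SAP wording and one additional disposition panel. Protocol 11.4 already requires the dates and reasons for both events in the CRF, so no new data are needed.

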3 STUDY ACTIVITIES

The study flowchart for the current version of the protocol is presented below.

3.1 Study Activities (Year 1 Visits)

Tests and Assessments ¹	Baseline Visit (Day 1) ²	Visit 1 (Week 4 ±5 days)	Visit 2 (Week 8 ±5 days)	Visit 3 (Week 12 ±5 days)	Visit 4 (Week 16 ±5 days)	Visit 5 (Week 20 ±5 days)	Visit 6 (Week 24 ±5 days)	Visit 7 (Week 36 ±7 days)	Visit 8 (Week 48 ±7 days)	
Informed Consent	X		,		,	,		,		
Randomization	X									
Medical History Update	X									
Physical Examination	X						X		X	
Vital Signs	X	X	X	X	X	X	X	X	X	
Hematology	X			X			X	X	X	
Blood Chemistry	X	X	X	X	X	X	X	X	X	
Urine Pregnancy Test ³	X	X	X	X	X	X	X	X	X	
Urinalysis	X	X^4	X^4	X^4	X^4	X^4	X^4	X^4	X^4	
Brain MRI ⁵ Scan ± Gd ⁶			Scheduled MR	I scans were pe	erformed in pro	otocol version	s 1 through 6.			
EDSS	X			X^7			X		X	
Visual Function Test	X						X		X	
SF-36 and EQ-5D	X								X	
Dispense Study Treatment (BG00012)	X	X	X	X	X	X	X	X	X	
Concomitant Therapy and Procedures Recording Monitor and record throughout the study as per Protocol Section 11.6										
AE/SAE Reporting			Monitor	and record thro	oughout the st	udy as per Pro	tocol Section	15		

AE = adverse event; EDSS = Expanded Disability Status Scale; EQ-5D = EuroQol EQ-5D Health Survey; Gd = gadolinium; MRI = magnetic resonance imaging; SAE = serious

adverse event; SF-36 = Short-form 36 Health Survey.

- 1. Tests and assessments must be completed prior to BG00012 distribution.
- 2. The Week 96 visit (Visit 24) for 109MS301 and 109MS302 will serve as the Baseline Visit for this extension study; activities should be completed (where appropriate) by staff of the parent study.
- 3. For women of childbearing potential. Results must be known prior to BG00012 distribution.
- 4. If urinalysis is abnormal, see Protocol Section 11.2.
- 5. Only in subjects who had MRI scans as part of Studies 109MS301 and 109MS302 and in 109MS303 up through and including Amendment 6.
- 6. MRI must not be performed within 30 days of receiving a course of steroids.
- 7. rmed only for subjects who at the Week 96 visit (Visit 24) in 109MS301 or 109MS302 had a 1.0 point increase in their EDSS score from a baseline EDSS \(\square\$ 1.0 or a 1.5 point increase in their EDSS from a baseline EDSS = 0.

